Title: PRMRP Norms: Iterative Design of Custom Dynamic Orthoses and Comprehensive Design of Musculoskeletal Model.

NCT Number: NCT04800510

Date: November 7, 2023

Study Protocol:

Purpose and Procedures:

The purpose of this study is to determine the effect of external bracing, in the form of a carbon fiber dynamic orthosis, on joint contact stress, muscle forces, physical function, and gait biomechanics. The effects of external bracing on gait mechanics, mobility, and muscle and joint forces are poorly understood. Collected data will include patient demographics and anthropometrics, ankle range of motion and stiffness data, plantarflexion strength data, CT images, CDO stiffness data, physical performance measures, patient reported outcomes, gait kinematics and kinetics, plantar pressures, and electromyography data. The knowledge that will be gained from this investigation has the potential to substantially improve the understanding of how external bracing impacts limb function and inform future investigations to advance the clinical prescription of ankle foot orthoses.

Objectives and Specific Aims:

Specific Aim 1: Determine the effect of CDO design modifications on ankle contact stress in a cohort of healthy able-bodied individuals.

Specific Aim 2: Determine the effect of CDO design modifications on physical function and gait biomechanics in a cohort of healthy able-bodied individuals.

Specific Aim 3: Determine the effect of CDO design modification on muscle forces during gait

Specific Aim 4: Refine methods of integrating data from multiple sources into musculoskeletal model to evaluate ankle contact stress.

Background and Significance:

Post-traumatic osteo-arthritis (PTOA) is a significant problem caused by chronic, increased, contact stress and fracture severity. Surgical fracture reduction has been the mainstay of intra-articular fracture (IAF) treatment for decades, but it is not the only factor influencing joint contact stresses. Furthermore, even with the best surgical effort, there often remains residual incongruity that leads to elevated contact stress. Numerous studies have explored the relationship between elevated contact stresses and the development of osteoarthritis following traumatic injury of the ankle. CDOs, such as the Intrepid Dynamic Exoskeletal Orthosis (IDEO) developed at Brooke Army Medical Center, have been used to dramatically improve function and reduce pain in hundreds of service members with traumatic limb injury. CDOs are comprised of a proximal cuff sitting just below the knee, a posterior strut used to store and return energy, a semi-rigid foot plate, and in some cases a heel cushion between the footplate and shoe [11]. These design components can be varied to influence the forces and motions experienced by the limb [11-14], which in turn influence the forces on the foot and the activation of muscles that cross the ankle [8, 15, 16]. Recent findings indicate that this can decrease load transfer across the ankle, which implies that CDOs may be able to be effectively tuned to reduce articular contact stress. A key mechanism by which articular contact stress may be reduced is the reduction of force produced by muscles around the ankle.

The multiple data sources collected in this study will serve as inputs for creating a comprehensive musculoskeletal model using OpenSim modeling software. OpenSim is an extensible software package that has been developed over decades to combine knowledge of computational modeling and biomechanical system simulations in order to calculate muscle forces generated from movement, kinematic adaptations during gait, and human-device interactions [78]. The use of OpenSim will allow for accurate simulations of gait, as well as calculation and prediction of variables that are difficult to measure experimentally [78].

Inclusion/Exclusion Criteria:

Patient Inclusion Criteria

- Between the ages of 18 and 50
- Shoe size between women's 8 and 13.5 or men's 6.5 and 12
- Healthy individuals without a current complaint of lower extremity pain, spine pain, or medical

or neuromusculoskeletal disorders that have limited participation in work or exercise in the last 6 months

- Full active range of motion of the bilateral lower extremities and spine
- Ability to hop without pain
- Ability to perform a full squat without pain
- Ability to read and write in English and provide written informed consent

Patient Exclusion Criteria

- Diagnosed moderate or severe brain injury
- Prior lower extremity injury resulting in surgery or limiting function for greater than 6 weeks
- Diagnosis of a physical or psychological condition that would preclude testing (e.g. cardiac condition, clotting disorder, pulmonary condition)
- Visual or hearing impairment that would interfere with instructions given during testing
- Require an assistive device
- Wounds to the foot or calf that would prevent CDO use
- BMI greater than 35
- Pregnancy – Per participant self-report. Due to the expected small number of pregnant individuals and resulting inability to account for its effect on resulting outcomes, participants will be withdrawn from the study

Design and Methods:

Patients will wear generic sized CDOs provided by Bio-Mechanical Composites (Des Moines, IA). Personal/demographic and anthropometric information will be used to fully characterize the study participants. We will collect multiple variables that have been previously associated with outcomes including race, ethnicity, and education. Anthropometric and demographic information such as age, biological sex, study limb (left or right), height, weight, leg length, shoe type, shoe length and width will also be used to characterize the cohort. Multiple outcomes measures will be used to characterize patient-centric outcomes.

Physical performance measures provide an objective and responsive assessment of an individual's functional mobility. Activities of daily life require performance of a range of functional tasks that require balance, agility, speed, and power. The four square step test (4SST) is a widely used test of functional mobility that requires rapid changes in direction that are often problematic following lower limb injury. The measure has good to excellent reliability and validity across multiple patient populations and groups and is a key dependent measure in most CDO-related studies to date and has demonstrated ability to detect changes in function in individuals with limb trauma and CDOs [7, 9, 27, 36]. The sit to stand 5 times (STS5) test is a well-established measure of lower limb muscle strength, endurance, and mobility [39]. The STS5 test has excellent reliability and good validity across a broad range of patient populations [35, 39-48].

Patient-reported outcomes questionnaires will be used to evaluate participant physical function, activity level, pain, comfort, satisfaction, and preference in addition to multiple other relevant outcomes. The Orthotics Prosthetics Users' Survey (OPUS) is a leading measure for evaluating satisfaction with orthotic devices and services [49]. It is a self-report questionnaire, with the full battery consisting of 88 questions and five modules. The satisfaction with devices portion will be used to evaluate device comfort, form, and fit using a four-point Likert scale and has good to excellent reliability, internal consistency, and validity for individuals with a wide range of diagnoses requiring orthotic and prosthetic services [49]. Comfort and smoothness will also be assessed using a modified version of the Socket Comfort Score, a reliable, valid, and sensitive measure of device fit and comfort [50]. These measures have been shown to effectively capture patient perception, are

responsive to simple modifications to CDO device function, and will be applied in a manner consistent with a prior publication by the research team [11]. Participants will be asked to report their pain using a standard 11-point numerical pain rating scale, in which 0 = no pain and 10 = worst pain imaginable, at the start of each session, and at multiple points while walking in each condition. Participants will be asked to rate the three braces (CDO-A, CDO-B, and CDO-C) on a standard 11-point scale, where 0 = worst imaginable device and 10 = best imaginable device. The University of California, Los Angeles (UCLA) activity score is a 10-level rating scale that is used to both qualitatively and quantitatively define an individual's current and/or desired level of activity and has been shown to be reliable with no floor effects [53]. The Patient Reported Outcomes Measurement Information System (PROMIS) is a group of patient-centered tests, developed through funding from the National Institutes of Health, which can be used to characterize physical, mental, and social health and function. The PROMIS instruments use modern measurement theory to reliably and validly assess patient-reported outcomes. We will use PROMIS to evaluate physical function. Semi-structured interviews will also be used to fully capture the patients' perspectives, experience, and opinions associated with the device options they experienced as part of the study.

Impairment, biomechanical, and device data will be used to compare devices, characterize limb and device function, and to provide insight in a manner not commonly found in comparative studies. Bending stiffness will be measured using a custom-made orthotic stiffness testing device designed specifically for quantifying CDO bending stiffness in Nm/degree. Ground reaction force and motion capture data will be used to evaluate the motion and loading of the lower limb and CDO devices as participants walk on an over ground walkway at self-selected speed and a controlled speed based on leg length [54, 55]. Muscle activity will be measured using DELSYS EMG sensors. EMG data will be collected bilaterally in the lower limbs and data will be analyzed over regions throughout the gait cycle. In-shoe plantar pressure distribution will be measured using the LoadSol system which interfaces with the foot and shoe insole and has been found to be accurate, precise, and repeatable in measuring plantar pressures during normal gait [60, 61]. Ankle range of motion and stiffness will be assessed using the Iowa Ankle Range of Motion device. Ankle strength will be assessed using the Standing Heel-Rise Test. Subjects will perform as many standing heel-rises as they can, while their ankle motion and body/limb alignment are carefully monitored.

Statistical Analysis Plan:

Analysis Methods:

Data quality will be rigorously examined over the course of this study. The distributions of study measures will be characterized using descriptive statistics. For descriptive statistics, univariate statistical approaches will include careful review of data frequencies, measures of central tendency, and distribution shapes. Additionally, identification of out of range data, determination of the quantity of missing data, and accurate description of the study population will be achieved.

Power Analysis:

The proposed sample size for this study is 10 subjects. Since the primary purpose of this study is to refine procedures for inputting multiple data sources into a musculoskeletal model, the study does not call for a total number of participants consistent with prior investigations by [name]. In a 2017 study conducted by Blazkiewicz et al, data was collected from 10 healthy subjects and incorporated into a generic OpenSim musculoskeletal model [79]. The results of the study showed some inter-individual variation as expected, but identified a common theme of muscle peak force regularities acting on the ankle joint across subjects, indicating that a 10 subject sample size is sufficient for the protocol design of similar investigations [79].

References Cited:

1. Anderson, D.D., et al., Intra-articular contact stress distributions at the ankle throughout stance phase-patient-specific finite element analysis as a metric of degeneration propensity. *Biomech Model Mechanobiol*, 2006. 5(2-3): p. 82-9.
2. Anderson, D.D., J.L. Marsh, and T.D. Brown, The pathomechanical etiology of post-traumatic osteoarthritis following intraarticular fractures. *Iowa Orthop J*, 2011. 31: p. 1-20.
3. Kern, A.M. and D.D. Anderson, Expedited patient-specific assessment of contact stress exposure in the ankle joint following definitive articular fracture reduction. *J Biomech*, 2015. 48(12): p. 3427-32.
4. Anderson, D.D., et al., Expedited CT-Based Methods for Evaluating Fracture Severity to Assess Risk of Post-Traumatic Osteoarthritis After Articular Fractures. *Iowa Orthop J*, 2016. 36: p. 46-52.
5. Anderson, D.D., et al., Is elevated contact stress predictive of post-traumatic osteoarthritis for imprecisely reduced tibial plafond fractures? *J Orthop Res*, 2011. 29(1): p. 33-9.
6. Amorelli, C.R., et al., Center for the Intrepid: Providing Patients POWER. *US Army Med Dep J*, 2016: p. 39-46.
7. Bedigrew, K.M., et al., Can an integrated orthotic and rehabilitation program decrease pain and improve function after lower extremity trauma? *Clin Orthop Relat Res*, 2014. 472(10): p. 3017-25.
8. Brown, S.E., E. Russell Esposito, and J.M. Wilken, The effect of ankle foot orthosis alignment on walking in individuals treated for traumatic lower extremity injuries. *J Biomech*, 2017. 61: p. 51-57.
9. Hsu, J.R., et al., Patient Response to an Integrated Orthotic and Rehabilitation Initiative for Traumatic Injuries: The PRIORITY-MTF Study. *J Orthop Trauma*, 2017. 31 Suppl 1: p. S56-S62.

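### Do the two statements of the study's purpose conflict in a way that undermines the sample size of 10 or the planned comparisons?

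*Combined protocol and SAP*

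**What the plan says.** The Purpose and Procedures section opens with "The purpose of this study is to determine the effect of external bracing, in the form of a carbon fiber dynamic orthosis" and names joint contact stress, muscle forces, physical function and gait biomechanics as the outcomes. Objectives and Specific Aims then lists four aims. Aims 1 to 3 ask how modifications to the carbon fiber orthosis (CDO) design affect contact stress, function and gait, and muscle forces. Aim 4 is to refine how data from several sources enter the musculoskeletal model.

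The Power Analysis proposes 10 subjects. It states that "the primary purpose of this study is to refine procedures for inputting multiple data sources into a musculoskeletal model", and that for this reason "the study does not call for a total number of participants consistent with prior investigations". Its precedent is one earlier modelling study of 10 healthy subjects, which it says "identified a common theme of muscle peak force regularities acting on the ankle joint across subjects".

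Design and Methods gives the test conditions piecemeal. Participants will "rate the three braces (CDO-A, CDO-B, and CDO-C") on an 11-point scale. Pain is recorded "at the start of each session, and at multiple points while walking in each condition". For gait, "participants walk on an over ground walkway at self-selected speed and a controlled speed based on leg length". The stated use of the data is: "Impairment, biomechanical, and device data will be used to compare devices, characterize limb and device function, and to provide insight". Analysis Methods is limited to descriptive statistics and checks of data quality.

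**The concern.** The two purpose sentences put different objectives first. The one in the Power Analysis corresponds to the last of the four aims and does not appear in the opening purpose sentence. It is also the only reason given for not matching earlier sample sizes. The precedent, as described, involves no brace comparison. If the opening sentence governs, a sample size of 10 has no stated argument for a bracing or design contrast.

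The conditions add to the doubt. Taken literally, an effect of bracing needs an unbraced reference, and none is stated or excluded. The three braces appear only as labels in a rating item, how they differ is not described, and the phrase about walking in each condition is not tied to a list. A reader might then be unsure whether a reported effect is primary or exploratory, and which contrast produced it.

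**Working it through.** **The plan's own figure.** The only figure is the sample size of 10. No alpha, power, effect size, SD or dropout rate is attached, so there is no calculation to reproduce. It is a choice by precedent.

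**The purposes side by side.**

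| Place | What leads |
|---|---|
| Title | Both strands: orthosis design and musculoskeletal model |
| Purpose and Procedures | Effect of external bracing |
| Aims 1 to 3 | Effect of orthosis design modifications |
| Aim 4 | Refinement of model inputs, in order to evaluate ankle contact stress |
| Background and Significance | The collected data feed the OpenSim model |
| Power Analysis | Refinement of model inputs |

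By count, 3 of 4 aims concern design modifications, 1 of 4 concerns the model, and 0 of 4 name braced versus unbraced. The strands are nested: the data collected in the braces are the inputs to the model, and Aim 4 serves the outcome of Aim 1. What the text leaves open is the ranking.

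**Which contrast is meant.** Aims 1 to 3 and the stated intention to compare devices both point to brace against brace. The possible condition lists give:

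- three braces: 3 × 2 / 2 = 3 pairwise contrasts, 0 of them braced versus unbraced;
- three braces plus an unbraced condition: 4 × 3 / 2 = 6 contrasts, 3 of them braced versus unbraced.

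The 3 brace-to-brace contrasts exist under both lists, so Aims 1 to 3 can be addressed either way.

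**What 10 people give, for scale only.** The half-width of a confidence interval for a paired mean difference, in SD of the paired differences, is t / √n. With n = 10, df = 9 and √10 = 3.162:

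- 90%: 1.833 / 3.162 = 0.58
- 95%: 2.262 / 3.162 = 0.72
- 95% with Bonferroni adjustment for three contrasts: 2.933 / 3.162 = 0.93

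At 95%, 9 complete cases give 0.77 and 8 give 0.84. A paired t-test at two-sided 0.05 with 10 people has 80% power for a difference of 1.00 SD with one comparison, and 1.22 SD with Bonferroni for three.

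The confidence levels, the adjustment, the power target and the numbers of complete cases are assumptions. The documents give no SD, so none of this converts to outcome units. The formula does not contain the purpose: a brace-to-brace and a braced-to-unbraced contrast have the same width in these units. The figures describe a small study and do not measure the mismatch between the two sentences.

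**Does the ranking change any planned result?** The Statistical Analysis Plan specifies distributions, central tendency, out-of-range values, missing data and a description of the population. It allocates no alpha, tests no hypothesis and sets no decision rule. The same summaries are produced whichever purpose is put first.

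**The case for a change.** The strongest case for a change is that it would cost only a few sentences and that the sample size argument depends on the ranking. The Power Analysis reasons from the modelling purpose to the smaller number, and no size argument is offered for Aims 1 to 3. The opening paragraph returns more than once to the effects of external bracing, so its wording is not a stray phrase. A purpose stated as the effect of bracing could lead a report to claim a braced-versus-unbraced effect that the data may not contain.

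Much of this stands as description. The leading purposes do differ, the departure from earlier sample sizes is argued only from modelling, and the conditions are not collected in one place. Three points limit it. First, the opening sentence does not call its purpose primary, and external bracing can be read as the umbrella topic for Aims 1 to 3. Second, the precedent concerns muscle forces at the ankle in healthy people, which touches the opening purpose and Aim 3 as well as Aim 4, although it gives no support for a brace contrast. Third, three braces and two walking speeds are named, so the conditions are partly given. The only suggested addition to the analysis, braced-minus-unbraced differences with intervals, would depend on data that the documents neither promise nor exclude.

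**Conclusion.** The concern does not call for a change. Two sentences differ on which purpose leads, and one reference to conditions is undefined. Neither makes a stated figure or rule wrong, blocks any of the four aims, or alters a descriptive summary. Because no power or error rate is claimed for Aims 1 to 3, the sample size of 10 is not contradicted by the lack of an argument for them. It simply supports no confirmatory claim about them, and the plan makes none.

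Analysts can fill the gap sensibly: take the contrasts from Aims 1 to 3, treat them as descriptive, and describe an effect of bracing as such only if unbraced walking was recorded.

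This rests on reading the analysis as descriptive, as Analysis Methods is written, and on the aims defining the contrasts. If the study later claimed a confirmatory effect of bracing, the missing size argument would matter. The half-widths of 0.58 to 0.93 SD are context under assumed inputs and carry no weight in this conclusion.

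### Aims 1 to 3 ask for the effect of CDO design changes, but the only statistical analysis stated is univariate description, which gives no within-participant device difference and no measure of its precision

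*Combined protocol and SAP*

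**What the plan says.** Purpose and Procedures frames the study as a question about an effect: "The purpose of this study is to determine the effect of external bracing, in the form of a carbon fiber dynamic orthosis". The outcomes named there range from contact stress in the joint to gait. Objectives and Specific Aims repeats this framing three times. Contact stress comes first: "Specific Aim 1: Determine the effect of CDO design modifications on ankle contact stress in a cohort of healthy able-bodied individuals". The next objective turns to function and walking: "Specific Aim 2: Determine the effect of CDO design modifications on physical function and gait biomechanics in a cohort of healthy able-bodied individuals". A third objective, in the same form, deals with the muscles: "Specific Aim 3: Determine the effect of CDO design modification on muscle forces during gait". The remaining aim, the fourth, is different in kind and concerns refining the modelling method.

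Design and Methods indicates that participants meet more than one device. "Participants will be asked to rate the three braces (CDO-A, CDO-B, and CDO-C) on a standard 11-point scale". Pain is recorded when a session begins and then "at multiple points while walking in each condition". The interviews cover "opinions associated with the device options they experienced as part of the study". The same section says that impairment, biomechanical and device data will serve to compare the devices, but attaches no method to that statement.

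The Analysis Methods part of the SAP promises scrutiny of data quality and a descriptive account of each measure's distribution. It then says: "For descriptive statistics, univariate statistical approaches will include careful review of data frequencies, measures of central tendency, and distribution shapes". It closes with out-of-range values, the amount of missing data and a description of the study population. Power Analysis gives a sample size of 10, justified by one earlier modelling study of 10 healthy subjects, and names refinement of the modelling inputs as the primary purpose.

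**The concern.** An effect of a design modification is a difference between conditions. Univariate summaries describe one variable at a time. If the same people are measured in several devices, the precision of a device difference depends on how each person's values move together across devices, and separate means and SDs do not carry that information.

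The plan would therefore leave three of its four aims without a statement of how precisely any effect is known. With 10 participants, bare means are easily over-read. The contrasts and the estimator also stay open until after the data are seen.

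**Working it through.** **The plan's own figure.** The sample size of 10 rests on precedent. The documents give no alpha, power, effect size, SD or dropout allowance, so it cannot be reproduced by calculation. What can be computed is the precision that 10 participants would give.

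**Aims against analysis.**

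| Aim | What it asks for | Statistical method stated |
|---|---|---|
| 1 | Effect of design changes on contact stress | Univariate description |
| 2 | Effect on physical function and gait | Univariate description |
| 3 | Effect on muscle forces | Univariate description |
| 4 | Refinement of the modelling method | Not an effect question |

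Design and Methods also says that EMG data are analysed by region of the gait cycle, and the background describes calculating muscle forces in OpenSim. These steps produce outcome values; neither compares devices.

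**Precision of a paired difference** (two-sided 95% interval, complete pairs). Half-width = t(0.975, n−1) × SD_diff / √n.

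- n = 10: 2.262 / 3.162 = 0.715 × SD_diff
- n = 9: 2.306 / 3 = 0.769 × SD_diff
- n = 8: 2.365 / 2.828 = 0.836 × SD_diff

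These factors depend only on n. SD_diff must come from the data, and per-device summaries do not contain it.

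**Why per-device summaries are not enough (illustration).** Assume the same SD s in each device, n = 10, and a between-device correlation rho. The documents give no rho, so a range is shown. SD_diff = s × √(2(1 − rho)).

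| rho (assumed) | SD_diff | Half-width |
|---|---|---|
| 0 | 1.41s | 1.01s |
| 0.5 | 1.00s | 0.72s |
| 0.8 | 0.63s | 0.45s |
| 0.9 | 0.45s | 0.32s |

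Identical per-device means and SDs are thus compatible with intervals whose widths differ by 1.012 / 0.320 = 3.2-fold across this range.

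Treating the summaries as independent groups would give t(0.975, 18) × √(2/10) = 2.101 × 0.447 = 0.94s whatever rho is. The paired interval is narrower once rho exceeds 1 − (2.101/2.262)² = 0.137.

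**Ordinal ratings.** For n = 10 without ties, the signed-rank interval runs from the 9th to the 47th of the 55 ordered Walsh averages, with coverage 1 − 2 × 0.0244 = 95.1%. Ties on an 11-point scale make it conservative.

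**The case against.** The strongest reply is that this is a study of 10 healthy volunteers whose declared primary purpose is to refine a model. Description suits that purpose, no safety or enrolment decision depends on the device comparisons, and paired intervals could be computed later from the same participant-level data. This stands as a limit on severity. It does not close the gap, because Power Analysis does not withdraw Aims 1 to 3, and those aims still promise an effect.

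Several stronger readings are tempting, and the documents do not support them:

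- *The plan rules out paired analysis, or proposes to treat devices as independent groups.* It does neither. The wording of Analysis Methods is not exhaustive. The fault is that no contrast is specified.
- *No analysis other than descriptive summaries is planned.* Musculoskeletal modelling, EMG analysis and interviews are also described. The accurate statement is that description is the only statistical analysis stated.
- *Every outcome is certainly measured in every device.* This is explicit only for the brace ratings and, by condition, for pain. For contact stress, muscle force, gait and performance tests it is the natural reading, but it is inferred.
- *The 3.2-fold range measures harm to this trial.* It follows from the assumed values of rho. It shows only that per-device summaries cannot determine a paired interval.

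One caution also stands against the remedy. Contact stress and muscle force are model outputs, and the modelling method is itself under refinement in Aim 4. A paired interval reflects variation between participants and excludes error shared through the model, so it could suggest more certainty than exists.

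**Conclusion.** The mismatch between aims and analysis is real and should be fixed. Followed as written, the SAP yields no within-participant device difference and no measure of its precision for Aims 1 to 3, although the study is said to compare devices. With 10 complete pairs the missing interval would have a half-width of 0.715 times the SD of the differences, or 0.836 times with 8 pairs. These factors would apply to any paired study of that size; the documents give no SD or precision target with which to express them in outcome units.

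A reader might infer that the study as a whole fails, or that it needs more participants or formal hypothesis tests. Neither follows: the primary purpose is unaffected, and exploratory estimates with intervals are enough. The conclusion assumes that the main outcomes are recorded in more than one condition per participant, as the section on brace ratings and pain suggests.

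**What to change.** Add to Analysis Methods text to this effect:

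*For one named main outcome for each of Aims 1, 2 and 3, and for the brace ratings, where measured in more than one condition, the within-participant difference will be reported for each pair of CDO-A, CDO-B and CDO-C, and for each CDO against no brace if that condition is tested. Each difference will be given with the number of pairs, the SD of the differences and a 95% confidence interval from paired differences: t-based for continuous outcomes, and the Hodges-Lehmann estimate with a signed-rank interval for ordinal ratings. These comparisons are exploratory and unadjusted for multiplicity. Intervals for modelled contact stress and muscle force reflect variation between participants and not model error.*

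Three braces give 3 pairwise contrasts per outcome, or 6 with a no-brace condition, so naming one main outcome per aim keeps the list short. If only summaries are intended, the alternative is to reword Aims 1 to 3 so that they promise description and not an effect.

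The cost is SAP wording and a modest amount of extra analysis. No new data are needed if, as appears, the outcomes are measured in each condition; the sponsor should confirm this. There are two small statistical costs. A participant who misses a condition drops out of the pairs involving it. If the correlation between conditions were below about 0.14, a paired interval would be slightly wider than an unpaired one (1.01s against 0.94s at rho 0).

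### Does a purely descriptive SAP fail the model-refinement purpose that the Power Analysis calls primary?

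*Combined protocol and SAP*

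**What the plan says.** Two sections state the purpose differently. Purpose and Procedures opens with "The purpose of this study is to determine the effect of external bracing, in the form of a carbon fiber dynamic orthosis", and goes on to name contact stress, muscle forces, function and gait. The Power Analysis says that "the primary purpose of this study is to refine procedures for inputting multiple data sources into a musculoskeletal model", and uses this to explain why fewer participants are needed than in previous work. The number 10 is then supported by one published modelling study with 10 healthy participants.

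Under Objectives and Specific Aims, Aims 1 to 3 concern the effect of orthosis design changes. The last aim is the modelling one: "Specific Aim 4: Refine methods of integrating data from multiple sources into musculoskeletal model to evaluate ankle contact stress".

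Background and Significance says: "The multiple data sources collected in this study will serve as inputs for creating a comprehensive musculoskeletal model using OpenSim modeling software". It adds: "The use of OpenSim will allow for accurate simulations of gait, as well as calculation and prediction of variables that are difficult to measure experimentally". The data to be collected include "physical performance measures, patient reported outcomes, gait kinematics and kinetics, plantar pressures, and electromyography data".

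Design and Methods states that "Impairment, biomechanical, and device data will be used to compare devices", and three braces are tested: "Participants will be asked to rate the three braces (CDO-A, CDO-B, and CDO-C) on a standard 11-point scale".

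Analysis Methods in the SAP names descriptive summaries of each measure (counts, averages, form of the distribution), checks for out-of-range and missing values, and a description of the participants. It names no other method.

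**The concern.** If improving the model inputs is the main goal, one expects the SAP to say how improvement will be recognised. One-variable summaries do not set one input procedure against another, or model output against a measured value. No error or agreement measure is listed among the study measures. The list of collected data mixes likely model inputs with questionnaires, so it does not show what feeds the model and what could check it.

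Aims 1 and 3 appear to take their results from the same model in the same 10 people, and nothing says that the model is fixed before the braces are contrasted. If the bracing purpose governs instead, the reason given for 10 participants does not cover it. At stake would be an unsupported claim of accuracy, or a sample size defended by the wrong goal.

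**Working it through.** **1. The plan's own figure.** The sample size of 10 cannot be reproduced by formula. The Power Analysis gives no alpha, power, effect size or standard deviation; it relies on precedent.

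**2. How far the two purposes conflict.** Of the four aims, three concern device effects and one (Aim 4) is modelling. The study title also names both the orthosis design and the musculoskeletal model. Both purposes are therefore in the opening section. What differs is the rank: the Power Analysis puts modelling first, while the aims list it last without ranking anything.

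**3. What the modelling purpose requires.** Both the Power Analysis and Aim 4 speak of refining. No section defines alternative input procedures, a reference procedure or a comparison between them. A worked-out, documented way of combining the data sources meets that wording. If the analysts compute an error for each participant, that error is itself a variable, and a one-variable summary of it would be adequate.

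**4. What one-variable summaries cannot see.** Let 10 measured values have mean 0 and SD 1, and let the model outputs be the same 10 values assigned to participants in some other order. Mean, SD, shape, range and missing count are the same for every order. Agreement is not:

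RMSE = SD × √(2(1 − r))

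| r | RMSE in SD |
|---|---|
| 1 | √0 = 0 |
| 0.63 | √0.74 = 0.86 |
| 0 | √2 = 1.41 |
| −0.63 | √3.26 = 1.81 |
| −1 | √4 = 2.00 |

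Over 200,000 random orders of 10 normal scores, 95% of correlations lie between −0.63 and 0.63. These figures use the SD with divisor n; with divisor n − 1 each RMSE is multiplied by √(9/10) = 0.95. The arithmetic is right, but the only thing it takes from this study is n = 10. It describes marginal summaries in general. It does not compare two input procedures, and it assumes a measured counterpart on the same scale, which the documents do not supply for contact stress.

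**5. Would re-ranking the purposes change anything?** For illustration, assume a paired two-sided contrast in 10 people at alpha 0.05, with effects in SDs of the within-person difference (none of this is in the documents). The 95% interval has half-width 2.262/√10 = 0.72 SD. The effect detectable with 80% power is 1.00 SD by the noncentral t distribution; the normal approximation gives (1.960 + 0.842)/√10 = 0.89 SD. These values depend on n = 10 and are the same whichever purpose is called primary.

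**The case for a change.** The strongest case for a change is that the rank of the purposes does some work. The Power Analysis uses it to excuse a smaller study, so if bracing is the real purpose, the stated reason for 10 does not reach it. The SAP also gives no criterion by which anyone could say that the procedures were refined, while the Background speaks of accurate simulation. Most of the requested changes would be wording only.

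The textual part stands: the two sections disagree on rank, and no deliverable or criterion is written for Aim 4. The rest is weaker.

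- **Accuracy:** the sentence on accurate simulation describes what the software can do. It is not a stated result of this study.
- **Inputs:** analysts building a gait model will not enter satisfaction questionnaires into it, so a source-by-source list mainly records what they would do anyway.
- **Model version:** analysts would ordinarily run everyone through one final version, and nothing suggests that the model will be chosen on the brace results. The SAP plans no test, so there is no confirmatory claim to relabel.
- **Agreement measure:** comparing predicted activation with EMG would matter only if a claim of a better procedure were intended. The documents do not state the muscles or the normalisation, so the recordings may not support it. Agreement with EMG would not validate contact stress either.

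One related gap is real but separate. Design and Methods intends to compare devices, yet the SAP states no within-participant contrast of the three braces. That bears on Aims 1 to 3, and a criterion for model inputs would not close it.

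**Conclusion.** No change to the plan follows. The difference between Purpose and Procedures and the Power Analysis is an inconsistency of emphasis between two goals that both appear in the aims. Settling it would alter neither the 10 participants nor the data, and no error rate or power figure hangs on it. The missing criterion for Aim 4 is a gap that analysts can fill sensibly in a small methods-development study. The RMSE range of 0.86 to 1.81 SD shows what marginal summaries cannot detect in any study and should not be read as an error expected here.

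This rests on three assumptions: that Aim 4 will deliver a documented workflow, that no claim will be made that one input procedure is more accurate than another, and that all participants are processed with one final model version. If the report were to claim superior accuracy, an agreement measure chosen beforehand would be needed.
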